## 6.0 STUDY DESIGN

### 6.1 Overview of Study Design

This study will employ a single arm, multiple case study design using a mixed methods approach to examine the adoption, implementation, and reach of EIMG across Prisma Health primary care clinics (i.e., clinic workflow, referral process), leading to patient enrollment in a community-based, evidence-informed PA program. Eligible Prisma Health primary care clinics that have not yet received EIMG onboard training and activation will be provided with the opportunity to adopt EIMG as a part of their clinic practice and patient workflow process. A mixed methods approach will examine contextual factors influencing decisions to adopt/not adopt EIMG.

Clinic champions at clinics adopting EIMG will be provided with a brief pre-recorded training video to disseminate to their clinic staff (e.g., physicians, nurses, medical assistants, administrative assistants) on how to provide their patients with an EIMG referral. All providers at the clinic will have the ability to screen and identify physically inactive patients and provide them with an EIMG referral. Initial implementation and reach of EIMG at adopting clinics will be tracked for approximately four months following the dissemination of the pre-recorded training video. After four months, the EIMG team will provide a more in-depth, standardized clinic onboard training following established protocols iteratively developed and refined through the initial addition of EIMG clinics between 2016-19. The onboard training, which consists of an overall presentation of the EIMG program and specific information on placing the referral order and patient workflow, has been adapted for virtual environments due to its notable added benefits, including its recording to serve as an ongoing reference tool for those who cannot attend initial training and incoming staff. Implementation and reach of EIMG will be tracked for an additional four months after the onboard training.

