### **6.2.7 Rationale for Control Condition**

The selection of our control group was influenced by several factors. There are currently only 20 Prisma Health primary care clinics that have not received EIMG onboarding and activation and that are within 15 miles or less of a participating community PA facility. There are no other equivalent Prisma Health primary care clinics to serve as matched controls (i.e., via a stepped wedge design). We are then left with two groups of clinics to serve as controls. The first of these is using a within-clinic design and comparing patient health outcomes before and after the dissemination of the initial EIMG Instructional Video. Secondly, from past experiences, we anticipate that several of the 20 clinics will choose not to adopt EIMG and/or will be non-responsive to our invitation. As one of our study aims, we will evaluate contextual factors and differences between adopting and non-adopting clinics. Clinics that do not adopt EIMG will not be 'activated' and can therefore serve as control clinics, particularly when evaluating patient-level outcomes, as none of their patients will have had the opportunity to participate in EIMG.

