## 7.0 STUDY POPULATION

### 7.1 Prisma Health - Clinic Eligibility

As the unit of randomization, we will offer the opportunity to adopt EIMG to 20 Prisma Health primary care clinics that have not yet implemented EIMG. The department chairs for Internal and Family Medicine (Drs. [name] and [name]) have provided their support for EIMG expansion across these primary care clinics.

Eligibility criteria for clinics to participate in this study include the following:

- Prisma Health primary care clinics (i.e., family or internal medicine) located in the Upstate of South Carolina
- Have not received EIMG onboarding or activation in the past;
- Consist of at least two attending providers;
- Be located 15 miles or less from a participating community PA facility.

All potentially eligible Prisma Health primary care clinics were geographically coded to determine the distance to the nearest participating community PA facility. Clinics >15 miles will be ineligible for study participation as previous research consistently demonstrates that engagement in leisure time PA and enrollment in fitness centers is negatively correlated with distance to PA destinations.

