## **12.5 Secondary Aim 2**

To evaluate, from the health system perspective, the cost of implementing EIMG, employing variation from the step-wedge design to estimate the effect of EIMG vs. standard care on costs and outcomes (effectiveness). These estimates will be used to obtain the incremental cost-effectiveness of EIMG vs. standard of care.

*Hypothesis 2: Patients receiving an EIMG referral and participating in the 12-week, community-based PA program will experience improved health outcomes, decreased healthcare service utilization, and a reduction in health care expenditures compared to patients that do not receive an EIMG referral and the opportunity to participate in the PA program.*

[figure not shown]

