**12.5.5 Assessing the Effects of EIMG**

We will use episode of care level data generated using the quasi-experimental stepped wedge design to estimate the relationship between EIMG referral and study outcomes. Outcomes will include:

*Episode Healthcare Costs* – the price-weighted sum of all healthcare resources used by patient “i” during the episode of care

*Episode-Specific Health Outcomes* - Change in health outcomes (blood pressure; body weight; hemoglobin A1c; full lipid profile and physical activity for patient “i”) between the index visit and the first provider visit in the episode in the Outcome Period (Figure 6) in which this information is collected.

We will initially regress whether patients in an episode were referred to EIMG on variables representing whether the patient’s clinic had received standardized EIMG training, patient clinical and demographic characteristics, time trends, and clinic specific fixed effects represented by:

$$(2) \quad E_{ijk} = \beta_0 + \beta_1 \cdot X_{ijk} + \beta_2 \cdot L_j + \beta_3 \cdot M_k + \beta_4 \cdot C_{ijk} + \omega_j + u_k + \epsilon_{ijk}, \text{ where}$$

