$E_{ijk}$  equals 1 if patient “i” in the episode at clinic “j” in the “k-th” month after study initiation was referred to EIMG, 0 otherwise;  $X_{ijk}$  represents patient-specific baseline demographic, clinical, and socioeconomic factors,  $L_j$  are a series of binary variable for each Prisma clinic “j”,  $M_k$  is a count variable representing the number of months since the beginning the study that contains patient “i’s” index date, and  $C_{ijk}$  equals 1 if the episode occurred in a period in which the clinic “j” received or had previously received EIMG activation, 0 otherwise. The parameters  $\omega_j$ ,  $u_k$ , and  $\epsilon_{ijk}$  represent the model random effects associated with site “j”, month “k”, and patient “i”, respectively. We will estimate equation (1) using a generalized linear mixed model. The estimate of parameter  $\beta_4$  equals the effect of standardized EIMG training on the probability of the patient within the episode being referred to EIMG. Variables within  $X_{ijk}$  will include patient history of EIMG use. Our stepped wedge design will enable us to directly control for unmeasured factors associated with site and time. Secondary analyses will assess differences in the impact of standardized EIMG training by stratifying by eligible conditions (i.e., overweight/obese, hypertension, type 2 diabetes).

While EIMG activation will be randomly assigned to clinics using the stepped wedge design, actual EIMG referral decisions will remain at the discretion of provider and patient. As a result, referral decisions for some patients will be “non-compliant” at the clinical level. Providers may refer patients into EIMG based on factors unmeasured by the researcher that are related to study outcomes which can confound estimation of the effect of EIMG on study outcomes. With non-compliance, it is problematic to use “as treated” EIMG referral variation to assess the effects of EIMG referrals on study outcomes. Instrumental variable (IV) methods using randomized EIMG activation as an “instrument” will be used to avoid confounding problems. In this scenario IV estimation will yield consistent estimates of the effect of EIMG referral on study outcomes for the subset of patients whose referrals are responsive to the randomized clinical-level EIMG activation. This is known as the Complier Average Causal Effect (CACE). The CACE model is specified as:

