$$(3) \quad Y_{ijk} = \alpha_0 + \alpha_1 \cdot X_{ijk} + \alpha_2 \cdot L_j + \alpha_3 \cdot M_k + \alpha_4 \cdot \hat{E}_{ijk} + \rho_j + \tau_k + \vartheta_{ijk}, \text{ where}$$

$\hat{E}_i$  equals the *predicted probability* of that patient “i” is referred to EIMG from equation (2); and the other variables defined as in equation (2). The parameters  $\rho_j$ ,  $\tau_k$ , and  $\vartheta_{ijk}$  represent the random effects associated with site “j”, month “k”, and patient “i”, respectively. The estimated parameter  $\alpha_4$  on  $\hat{E}_{ijk}$  is the CACE or the average treatment effect for patient subset whose EIMG referral was influenced by EIMG activation at the clinic.  $C_{ijk}$  in equation (2) serves as the “instrument” and only the portion of variation in  $\hat{E}_{ijk}$  stemming from  $C_{ijk}$  is used to estimate  $\alpha_4$ . Because  $C_{ijk}$  will be randomly assigned, EIMG referral variation stemming from this assignment will be independent of unmeasured confounding variables. Two-stage least squares (2SLS) IV estimators will be used to estimate the effects of EIMG referrals induced by clinical-level EIMG activation on study outcomes. For each study outcome, equation (2) will serve as the first stage

equation of 2SLS, and second stage model will be equation (3). Because our expected sample sizes will be greater than 500 *our 2SLS estimates will be distributed normally via the central limit theorem regardless of the distribution of the underlying error term.* Each 2SLS model will be estimated with robust standard error methods appropriate for 2SLS models using STATA to account for error structure in equation (3).

Define  $\alpha_{4C}$  as the 2SLS estimate when episode healthcare cost is the dependent variable in equation (3) and  $\alpha_{4H}$  as the 2SLS estimate when a health outcome change is the dependent variable in equation (3). Combining these estimates with the estimates of average patient EIMG training costs from Section F3.2 yields the following cost-effectiveness ratio of EIMG relative to standard care:

$$(4) \text{ EIMG Cost Effectiveness Ratio} = \left[ \frac{(\text{EIMG Training Costs per Patient} + \alpha_{4C})}{\alpha_{4H}} \right]$$

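### Secondary Aim 2 rests its instrumental-variable analysis on a random stepped-wedge assignment that the design does not contain, and its cost-effectiveness ratio mixes two units

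*Combined protocol and SAP*

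**What the plan says.** The Aim 2 text relies on a randomised stepped wedge:

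- Section 12.5 states the aim as "employing variation from the step-wedge design to estimate the effect of EIMG vs. standard care on costs and outcomes".
- Section 12.5.5 describes "episode of care level data generated using the quasi-experimental stepped wedge design", then says "While EIMG activation will be randomly assigned to clinics using the stepped wedge design", and takes randomised activation as the instrument.
- Of the instrument C it says that it "will be randomly assigned, EIMG referral variation stemming from this assignment will be independent of unmeasured confounding variables".
- Section 7.1 begins its clinic criteria with "As the unit of randomization, we will offer the opportunity to adopt EIMG to 20" clinics.

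The design text does not:

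- Section 6.1: "This study will employ a single arm, multiple case study design".
- Section 6.2.7: "There are no other equivalent Prisma Health primary care clinics to serve as matched controls (i.e., via a stepped wedge design").
- Section 8.1: all eligible clinics are invited together, and stepped entry is excluded.
- Section 8.2.2: a clinic whose practice manager declines or cannot be reached becomes a non-adopter.
- Section 8.3: EHR access is switched on after the video goes to adopting clinics.

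For costs, equation (1) in 12.5.4 divides fixed plus variable training cost by the number of eligible patients over the study period. Equation (4) in 12.5.5 adds that figure to alpha_4C, the two-stage least squares (2SLS) cost effect of a referral, and divides by alpha_4H, the corresponding health effect.

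**The concern.** An instrument needs a reason to be unrelated to unmeasured causes of the outcome. The only reason given is random assignment, and no allocation list, ratio, sequence or crossover schedule appears in the document. Clinics that choose to adopt may differ from the others in how their patients' costs and risk factors would have changed anyway. Clinic indicators remove stable differences but not differences in change.

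If 12.5.5 is followed as written, the cost effect, the health effects and their ratio would be reported as protected from confounding by a randomisation that does not take place. Section 5.3 expects this economic evaluation to inform insurers' coverage decisions and health systems' adoption decisions.

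The unit mismatch in equation (4) is a separate error. It would remain even if activation had been randomised.

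**Working it through.** No stated figure needs reproducing for the first part. The question is what identifies C.

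**1. Identification of C.** Equation (2) contains clinic indicators L_j, a linear month count M_k and C. Section 10.0 has all adopters activate together at the start of month 2. A matrix-rank check, illustrated with 10 adopters and 10 non-adopters, gave:

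| Episodes in the model | C identified beside clinic indicators and linear month | C identified beside clinic indicators and month dummies |
|---|---|---|
| Adopters only, months 2-9 | no | no |
| Adopters and non-adopters, months 2-9 | no | no |
| Adopters only, with pre-activation months | yes, through linearity only | no |
| Adopters and non-adopters, with pre-activation months | yes | yes |

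The reasons are simple. Without a pre-period, C equals the sum of the adopters' clinic indicators. With adopters only, C equals the sum of the post-activation month indicators. Only the last row separates activation from calendar time, and it compares changes between two self-selected groups. It therefore needs parallel trends, which the plan does not state.

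**2. The pre-period is not defined.** Section 12.5.5 counts months from the start of the study, which leaves one month before activation. From 12.5.2, an episode runs 120 + 90 = 210 days after the index visit, so an episode indexed in that month extends well into the activated period. Section 6.1 foresees earlier EHR data, but 12.5 does not say how far back.

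The windows also interact with 12.5.1, which excludes an index date within 90 (taken as days) of the end of the patient's previous episode. As an example, assume 122-day windows and require only the 30-day referral decision period to end before activation (day 0):

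- Pre-activation index dates: day -152 to day -30.
- Episode ends: -152 + 210 = +58 to -30 + 210 = +180.
- Earliest new index date: +58 + 90 = +148 to +180 + 90 = +270.
- The post-activation window closes at day +122.

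Every patient with a pre-activation episode would be barred from the post-activation sample. If whole episodes must end by day 0, the exclusion still reaches day +90. The windows therefore have to be set together with the exclusion rule.

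**3. Units in equation (4).** Let T be training cost per eligible patient, b the first-stage effect (beta_4 of equation (2)), and RF_C and RF_H the effects of activation per eligible patient on cost and on health. With one instrument and linear 2SLS:

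- alpha_4C = RF_C / b and alpha_4H = RF_H / b
- Equation (4) as written: (T + RF_C/b) / (RF_H/b) = (b*T + RF_C) / RF_H
- Ratio on one unit, per eligible patient: (T + RF_C) / RF_H

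So T is multiplied by b. The plan gives no first stage per episode. The nearest figures are the 12.3 referral profiles, which are clinic-month rates:

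- Video months: (0.001 + 0.004 + 0.007 + 0.010)/4 = 0.0055
- Step profile, eight months: (0.022 + 0.140)/8 = 0.02025
- Accelerated profile, eight months: (0.022 + 0.120)/8 = 0.01775

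Over an assumed range of b = 0.01 to 0.04, equation (4) counts 1% to 4% of T. Equivalently, $1 per eligible patient corresponds to 1/0.04 = $25 up to 1/0.01 = $100 per induced referral, but equation (4) adds only $1.

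**4. Inference.** Section 12.5.5 argues normality from an expected sample above 500 and asks for robust errors that respect equation (3), without naming a cluster level. C varies by clinic, and there are at most 20 clinics.

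**The case against.** The best defence is that the fault lies in the justification and not in the model. Section 12.5.5 itself uses the word quasi-experimental. Equations (2) and (3) already carry clinic and time terms. Sections 6.1 and 6.2.7 already foresee before-and-after data and non-adopting clinics as controls. This largely stands: the model is close to a difference-in-differences. It does not rescue the independence claim, which is drawn expressly from random assignment.

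Four stronger readings are tempting, and the documents do not support them.

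- *The Aim 2 estimates will be badly biased because 2SLS multiplies any drift 25 to 100 times.* The documents give no clinic-level drift and no per-episode first stage. The standard error is scaled by the same factor, so drift relative to its standard error does not depend on the first stage. In equation (4) the first stage cancels between alpha_4C and alpha_4H; only the training-cost term is left mis-scaled.
- *Aim 2 cannot be estimated.* It can, if the foreseen pre-activation data and control clinics are used.
- *The primary result is compromised.* The section 12.2 model does not use the instrument.
- *Reading beta_4 as the effect of standardized training, when C is defined by activation, is a plain mistake.* The in-depth session comes later ("After four months, the EIMG team will provide a more in-depth, standardized clinic onboard training"), but the wording is not consistent. The section 2.0 narrative calls the video standardized and the onboard training tailored, while 6.1 calls the video a training video and the onboard training standardized. This is an ambiguity to settle.

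It is also fair to say that no dollar figure in the plan shows how large the training cost is, so the effect of the unit error on the final ratio is not known in money.

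**Conclusion.** Wrong as written, on two counts that follow from the text alone. First, 7.1, 12.5 and 12.5.5 rest on a randomised stepped wedge that 6.1, 6.2.7, 8.1, 8.2.2 and 8.3 exclude, so the stated ground for instrument validity is absent. What can be estimated is a non-randomised difference-in-differences, and only with pre-activation episodes and non-adopting clinics. How far self-selection would move the estimates cannot be determined from the documents.

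Second, equation (4) counts training cost at beta_4 times its value. That result is algebraic for linear 2SLS with one instrument; the 1-4% figure depends on the assumed first stage. The direction favours EIMG.

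Both should be fixed before analysis. They are confined to a secondary aim.

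**What to change.** 1. Delete the random-assignment, stepped-wedge and independence statements in 12.5 and 12.5.5, and the randomisation phrase in 7.1. State that activation is self-selected in one wave.
2. Specify Aim 2 as a non-randomised controlled before-after (difference-in-differences) analysis of pre- and post-activation episodes from adopting and non-adopting clinics, with clinic and month effects. State the parallel-trends assumption, and reconcile the comparison with the matched controls named in 6.1. Report any 2SLS estimate with that assumption and the exclusion restriction stated, not as free of confounding.
3. State the pre- and post-activation index windows, consistent with the episode lengths in 12.5.2 and the exclusion in 12.5.1, so that the exclusion does not change who is in the before and after samples. Set the final extraction at least 210 days after the last index visit, and reconcile this with 7.2, which extracts at the end of month 8.
4. Define C once, as activation or as onboard training, and interpret beta_4 to match.
5. Cluster standard errors by clinic with a small-cluster method such as the wild cluster bootstrap, and drop the argument from a sample above 500.
6. Put equation (4) on one unit: either the activation effect per eligible patient with training cost per eligible patient, or the effect per induced referral with training cost divided by induced referrals. In both, count only post-activation eligible episodes at activated clinics.

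Cost: a rewrite of these sections, a weaker causal claim for Aim 2, and an EHR extraction that reaches further back and runs to about seven months (210 days) after the last index visit. No new patients or visits are needed.

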#### 3.3 Integrating Physical Activity Pathways into Health Systems

Similar to the SBIRT model (Screening, Brief Intervention, and Referral to Treatment), an evidence-based, clinical strategy for addressing substance use disorders, Exercise is Medicine (EIM) is a comprehensive model for integrating PA in the clinic workflow. *EIM is not a PA intervention*, but a framework to improve the reach of evidence-based PA interventions by identifying and engaging patients that would benefit from increased PA. The individual components of the EIM model include: 1) assessing PA levels of patients, 2) providing brief PA counseling and/or a PA prescription, and 3) referring patients to PA resources for further guidance. In some instances, a ‘navigator’ or referral team is involved to increase referred patient engagement levels (Figure 2). As described below, the individual components of the “EIM model” have moderate-to-strong evidence bases. Prisma Health-Upstate is the first and only large health system in the world to attempt to integrate all EIM components into their clinic workflow, connecting patients with chronic diseases to community-based PA programs.

Figure 2. Comprehensive model for physical activity integration into health systems.

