### 3.3.2 Providing Physical Activity Prescriptions

The New Zealand Green Prescription is the best-known program involving health professionals giving patients a written/electronic PA prescription, leading to increased PA levels compared to verbal advice alone. Patients receiving a prescription, compared to usual care, were more likely to meet PA guidelines and achieve higher energy expenditure with benefits extending out 2-3 years. Outside of a few small trials, PA prescriptions have not been systematically integrated into U.S. health systems.

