### 4.3 EIMG Clinic Workflow

The EIMG Clinician Decision Modules are incorporated into the EHR as part of clinical workflow. The three Decision Modules include: 1) PA assessment, 2) PA prescription (through patient order sets), and 3) referral to a community PA facility.

**Module 1: PA Assessment.** Front office or nursing staff capture the patient's current PA behavior via the PAVS programmed into the EHR. The PAVS consists of two questions (“how many minutes per day do you exercise?” and “how many days per week?”) to determine if the patient is meeting national PA guidelines of 150 minutes of moderate intensity aerobic activity a week. The PAVS identifies ‘eligible’ patients, provides a best practice alert (BPA) through the EHR stating that the patient may qualify for EIMG, and prompts providers to discuss lifestyle behavior change.

**Module 2: PA Prescription.** The healthcare provider informs eligible patients about the EIMG program, reviews risks, and provides basic PA and health education by providing them with *EIM Rx for Health* handouts for exercising with chronic disease (e.g., obesity, diabetes, hypertension, peripheral artery disease), developed by experts in the field. The healthcare provider then electronically starts an ‘EIMG Order Set’ leading to the patient referral.

**Module 3: Patient Referral.** Through a series of EHR prompts confirming patient eligibility, the healthcare provider sends a referral to the *EIMG Referral Team*. All aspects of the EHR referral process are electronic, except a paper version of the EIMG Consent to Treat and the Release of Information that the patient must sign (either while in the clinic room or at the checkout counter) in order to continue.

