### **8.3 Phase II – EIMG Instructional Video**

Phase II will start with disseminating the EIMG Instructional Video to adopting clinics, followed by EIMG activation. The EIMG Instructional Video is intended to be a low-intensity strategy for disseminating information and guidance on EIMG and the PA referral pathway connecting Prisma Health primary care clinics and the community PA facilities. The EIMG Instructional Video is a brief (11-minute), voice-over PowerPoint presentation that provides information on: a) the origins of EIMG, b) the 12-week, community-based PA program, c) initial patient effectiveness results, and d) process for placing an EIMG referral. The EIMG Instructional Video will be sent to the practice managers at EIMG-adopting clinics for broader dissemination to all

clinic staff. After delivery of the EIMG Instructional Video to the practice managers, access to the EIMG referral process in the EHR is *'turned on'* (aka – EIMG activation) allowing clinic staff to electronically identify and engage with eligible patients.

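### Aim 2 instruments referral with clinic activation on random assignment alone. Activation has other routes to outcomes, any such effect is divided by a 1–4% referral rate, and equation (4) mixes per-eligible and per-referred costs

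*Combined protocol and SAP*

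**What the plan says.** Section 12.5.5 notes that referral stays at the discretion of provider and patient, so comparing patients as treated would be confounded. It therefore proposes "Instrumental variable (IV) methods using randomized EIMG activation as an" instrument. The instrument C "equals 1 if the episode occurred in a period in which the clinic" has been activated, then or earlier. Equation (2) is the first stage (referral E on C, patient covariates, clinic and month) and equation (3) the second. The plan concludes that "IV estimation will yield consistent estimates of the effect of EIMG referral on study outcomes" for patients whose referral responds to activation. The only validity argument is that "EIMG referral variation stemming from this assignment will be independent of unmeasured confounding variables".

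Equation (4) then divides training cost per patient plus alpha_4C by alpha_4H. Section 12.5.4 computes training cost per eligible patient.

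Other sections describe what reaches a clinic besides the referral:

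- Section 4.3: the Module 1 alert "prompts providers to discuss lifestyle behavior change". Module 2 gives eligible patients activity education and handouts. Referral is Module 3.
- Section 8.3: activation turns on the referral process in the EHR, "allowing clinic staff to electronically identify and engage with eligible patients".
- Section 8.4 and the synopsis narrative: training covers the PAVS activity screen and brief counselling as well as referral.
- Section 3.3.1: PAVS integration is reported to increase counselling as well as referral.
- Section 3.3: the separate components "have moderate-to-strong evidence bases".

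**The concern.** Two-stage least squares needs two things of C: independence from unmeasured confounders, and no route to the outcome except through E. Random assignment, even if it held, could supply only the first. The second is neither stated nor defended, and no sensitivity analysis covers its failure.

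A patient who is screened and counselled but not referred has C = 1 and E = 0. If that contact changes weight, blood pressure or service use, the change belongs to activation, but equation (3) credits it to the few who were referred. At the planned referral rates a very small average change among the non-referred becomes a large term in alpha_4.

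The 2SLS model is the only Aim 2 estimator specified for costs and health outcomes, and both of its results enter the cost-effectiveness ratio. Section 5.3 expects that evaluation to inform coverage and adoption decisions.

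**Working it through.** **Inputs.** Aim 2 gives no first-stage or power figure of its own. The referral rates come from Section 12.3: about 0.01 in pilot data before onboarding; 0.001 rising to 0.01 over months 1–4; a jump of 0.02; then about 0.04 at month 8. Referral is taken as zero where C = 0, since Section 6.2.7 says patients at non-adopting clinics cannot enter EIMG.

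**1. The plan's own figure.** Section 12.3 states 92% power with 10 clinics for the step of 0.02. A simulation used rates 0.001, 0.004, 0.007, 0.010, 0.030, 0.033, 0.036, 0.039, clinic and residual SDs of 0.01, a model with time and EIMG, two-sided 0.05, and 100 batches of 100 runs. It gave mean power 95.7% and minimum 91%. The plan reports the minimum, so the rates are read as intended. The interaction power figures did not reproduce, but nothing here uses them.

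**2. What alpha_4 estimates.** Let tau be the effect of referral and d the mean effect of activation on patients not referred.

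- Activation effect per eligible patient (reduced form, RF) = p × tau + (1 − p) × d
- alpha_4 = RF / p = tau + d × (1 − p)/p

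If d reaches every eligible patient, the added term is d/p.

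**3. The multiplier on d.**

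| First stage p | Source | (1 − p)/p | 1/p |
|---|---|---|---|
| 0.04 | planned, month 8 | 24 | 25 |
| 0.020 | mean of the eight rates above | 49 | 50 |
| about 0.015 | simulated equation (2), planned profile | about 65 | about 66 |
| 0.01 | pilot, and planned month 4 | 99 | 100 |

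The simulated first stage assumes 20 clinics, 10 adopting, 8 pre-activation months, 300 patients per clinic-month, clinic dummies and a linear month term. If C marked onboard training instead, the contrast would be 0.0345 − 0.0055 = 0.029, and 1/0.029 is about 34.

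**4. Scale, with d assumed.** Section 4.14 reports an uncontrolled 7 mmHg systolic fall in program participants and 35.4% enrolment among those referred. As an illustration, tau = −7 × 0.354 = −2.48 mmHg. With d = −0.1 mmHg:

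- p = 0.04: −2.48 − 0.1 × 24 = −4.9 (2.0 times tau)
- p about 0.015: about −9.0 (3.6 times tau)
- p = 0.01: −2.48 − 0.1 × 99 = −12.4 (5.0 times tau)

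Simulated 2SLS means were −5.0, −9.3 and −12.9, in line with the formula given the simulation noise.

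**5. Equation (4).** Let T be training cost per eligible patient, with RF_C and RF_H the reduced-form cost and health effects. When both models use the same episodes,

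(T + RF_C/p) / (RF_H/p) = (p × T + RF_C) / RF_H.

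The factor 1/p cancels between cost and effect. T is left multiplied by p, so it counts at about 1–4% of the weight it has in the per-eligible ratio (T + RF_C)/RF_H.

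Assumed values show the consequence: T = USD 10, RF_C = −USD 2, RF_H = −0.1 mmHg, p = 0.02. Equation (4) as written gives (10 − 100)/(−5) = 18, a net saving with lower pressure. Per eligible patient it is (10 − 2)/(−0.1) = −80, a net cost of USD 80 per mmHg lowered. Putting T on the referred scale (10/0.02 = 500) gives (500 − 100)/(−5) = −80 again, so the disagreement comes entirely from the units of T.

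**The case against.** The best defence is that the direct path may be small or absent.

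- Section 8.3 describes activation as turning on the referral process. PAVS entered the EHR in the rollout that began in 2016 (Section 4.1), and Section 12.5.3 collects activity levels at every index visit. The documents do not say whether PAVS and alerts are off in non-activated clinics.
- Module 2 ends in the order set that creates the referral, so its recipients may largely be the referred patients.
- The denominator is a diagnosis-code list (Section 7.4). It can include active patients whom PAVS would not flag.
- Section 12.5.5 defines C by activation but describes its coefficient as the effect of training. Under training coding, activation is already on in months 1–4 with C = 0, so part of the direct path would sit on both sides of the contrast.

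All of this stands as uncertainty about d. It does not supply the missing condition, and counselling and staff training still arrive with adoption.

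Three stronger readings are tempting and are not supported:

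- **That the whole IV estimate is 25 to 100 times too large.** The factor multiplies d, and the product is added to tau. The whole estimate would be inflated that much only if d equalled tau. For costs, d could have the opposite sign.
- **That Section 3.3.2 proves counselling alone works.** It says patients given a prescription, compared with usual care, "were more likely to meet PA guidelines and achieve higher energy expenditure". It also compares prescription with verbal advice, and does not isolate an alert-prompted conversation.
- **That the cost-effectiveness ratio carries a 25- to 100-fold error.** Step 5 shows that 1/p cancels; what remains is the scale of T.

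**Conclusion.** The unconditional consistency claim should not stand. The exclusion condition is unstated, and the protocol's own workflow makes it doubtful. Any direct effect d enters alpha_4 multiplied by 25 to 100 at the planned rates, or about 50 to 66 for a single pooled first stage under activation coding. The total bias cannot be given, because the documents supply neither size nor sign for d; it is zero if d = 0. The blood pressure and dollar values above are illustrations.

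The unit mismatch in equation (4) does not depend on d. It follows from the definitions in Sections 12.5.4 and 12.5.5 and weights training cost at about 1–4% of its per-eligible-patient value.

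The independence argument has its own difficulty. Section 12.5.5 calls activation randomised, while Sections 6.2.7, 8.1 and 8.2.2 have all clinics invited at once and choosing whether to adopt. That limits what any activation contrast can claim.

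This is a should-fix: Aim 2 is secondary, and the primary outcome, referral rate, is untouched.

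**What to change.** 1. Make the reduced form the main Aim 2 analysis: regress each outcome on C with the same patient, clinic and time terms in all eligible episodes. Report it as the association of activation with outcomes per eligible patient, and say that clinics chose to adopt. Counselling effects are then part of what is measured.
2. Build equation (4) from the reduced-form cost and health effects, so that every term is per eligible patient.
3. Keep 2SLS/CACE as a secondary analysis, labelled valid only if activation acts solely through referral. Show alpha_4 − d × (1 − p)/p over a stated range of d, and the d that would explain the whole estimate, RF/(1 − p). Remove the unconditional consistency claim.
4. State whether C marks activation or onboard training, and whether PAVS and alerts run in non-activated clinics.

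The cost is SAP wording and one further regression per outcome on the same data. The headline effect becomes smaller because it is averaged over all eligible patients, and the contrast by referral in Hypothesis 2 moves to the secondary analysis.
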